Week 1 and Week 8 Visits (~60 minutes): Participants will be asked to turn in their 3-day diet records. Relevant symptoms, weight, vitals, sleep quality, depressive symptoms, stress, pain and any additional relevant questionnaires will be evaluated. Additionally, up to 16 mL of blood will be taken to measure biomarkers in serum and a morning urine sample will be collected. Participants will be given their allotment of intervention products to consume each day and continue to wear their Garmin Watch.

Vital Signs (e.g., body temperature, pulse, and seated blood pressure) will be measured. After 3-5 minutes of rest, seated blood pressure will be measured twice with an automated cuff.

Sleep Quality will be evaluated using a validated self-report questionnaire the Pittsburgh Sleep Quality Index (PSQI).³⁸

Relevant Symptoms including gastrointestinal distress, appetite, pain etc., will be collected by self-report.

Blood (approximately 16 mL) will be collected by a trained phlebotomist using sterile procedures. Blood will be processed and stored at -80 degree C for future analyses. Batch analyses of planned biomarkers (e.g., kynurenine/tryptophan ratio and select inflammatory markers (e.g., C-reactive protein, interleukin-6, etc.) will be measured by a reputable lab (e.g., Quest or collaborators at the University of Connecticut).

Spot Urine (approximately 30 mL) will be collected, processed, and stored at -80 degree C for future analyses. We will aim to collect urine in the morning hours between 8-10 am to avoid the influence of the circadian rhythm on cortisol. Batch analyses of planned biomarkers (e.g., cortisol and melatonin.) will be measured by a reputable lab (e.g., Quest or collaborators at the University of Connecticut).

Depressive symptoms will be evaluated using a validated self-report questionnaire (e.g., the Center for Epidemiological Studies Depression Scale (CES-D),³⁹ the CESD-revised (CESD-R)⁴⁰ version, and/or the Patient Health Questionnaire-9 (PHQ-9)³⁶).

Stress will be evaluated by the validated 10-item questionnaire, the Perceived Stress Scale.⁴¹

Pain will be evaluated via a validated 24-item questionnaire, the Geriatric Pain Measure.⁴²

Additional Questionnaires will be administered to evaluate other aspects that are relevant to sleep to help characterize our study population (e.g., validated self-report questionnaires that measure anxiety, affect etc.)

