Optional Study Assessments: Participants will also have the option to partake in two optional study assessments as described below. These optional study assessments allow for further investigations of potential mechanisms relevant to sleep, including analysis of phenolic metabolites in urine and analysis of the gut microbiota in fecal samples.

24 Hour Urine Sample: If participants are willing, they will be asked to provide a 24 hour urine collection instead of the planned spot urine collection. This requires individuals to collect all of their urine for the 24 hours preceding select study visits using a provided urine container. Urine will be processed and frozen until analysis. Regardless of whether participants opt for the spot or the 24 hour urine sample, batch analyses of planned urinary biomarkers (e.g., cortisol and melatonin) will be measured by a reputable lab (e.g., Quest or collaborators at the University of Connecticut). The 24 hour urine sample will also be used to evaluate phenolic metabolites. Briefly, urine samples acidified with formic acid will be purified via solid phase extraction to isolate gut-microbially generated phenolic acid metabolites (and their subsequent phase II hepatic conjugates). Purified samples will be analyzed using LC-MS/MS with a triple-quad mass spectrometer to quantify metabolites by their specific parent to daughter ion mass transitions. Targeted metabolomics quantifies ~60 phenolics, gut microbially generated phenolic acid metabolites, and hepatic phase II metabolites of absorbed phenolics and phenolic acids.

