Fecal Sample: If participants are willing, they will be asked to collect at least 1 (no more than 3) separate fecal samples before select visits. Samples will be collected as is, in a sterile collection tube without any preservation medium that will be provided to participants. There will be a collection for select visits as indicated below. Participants will temporarily store the self-collected fecal samples in their own freezer (-17°C), and then transported to the lab at HSL for sample processing and long-term storage. Fecal microbiota will be analyzed using whole genome sequencing (WGS) to obtain a holistic representation of the microbes in the gut. WGS was chosen because it enables identification of microbes down to specific species or strain of bacteria whereas other methods only identify the genus level and avoid biases common with 16S rRNA sequencing. A reputable lab (e.g., the Microbial Omics Core at the Broad Institute) will perform the DNA extraction from fecal samples and WGS library construction and sequencing using NEBNext Ultra FS II (2x150bp sequencing chemistry to a minimum depth of 3 million reads per sample). Fastq sequences will be processed and analyzed by a reputable lab/core (e.g., the Harvard Chan Microbiome Analysis Core).

Optional Study Assessments

Visit	1	2	3	4	-	5	6	7
	Week 0	Week 1	Week 3	Week 5	Week 7	Week 8	Week 10	Week 12
24 Hour Urine Collection	X			X	X			X
Fecal Sample	X			X	X			X

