5.4 Outcome Measures

Our primary endpoints are aspects of feasibility. Secondary endpoints include sleep quantity and quality, as well as sleep-related biomarkers (e.g., melatonin, serotonin, cortisol, inflammatory markers). Exploratory outcomes include sleep-related factors (e.g., mood, stress, pain). We will also explore other alternative outcomes.

Name	Type	Timeframe	Brief description
Recruitment Rate	Primary	Throughout the entire study	Number of individuals that need to be screened to be enrolled that are randomized to the intervention.
Attrition	Primary	Throughout the entire study	Number of individuals randomized that withdraw from the intervention in media res .
Compliance of Dose	Primary	Throughout the entire study	The number of intended doses consumed.
Ability to Collect Data	Primary	Throughout the entire study	The percentage of missing data points from electronic capture data devices.
Practicality	Primary	Throughout the entire study	Self-reported willingness to continue the dietary regimen after study completion.
Sleep Quantity	Secondary	Throughout the entire study	Individuals will be asked to wear a polysomnographic device (e.g., Garmin

			watch) to continuously measure aspects related to sleep quantity (e.g., total sleep time, time spent awake).
Sleep Quality	Secondary	Week 1, 5, 8, 12	The validated self-report questionnaire, the Pittsburgh Sleep Quality Index, which ranges from 0-21 points.
Melatonin	Secondary	Week 1, 5, 8, 12	Melatonin will be estimated by measuring the major urinary metabolite of melatonin, 6-sulphatoxymelatonin, utilizing a commercially available quantitative immunoassay.
Serotonin	Secondary	Week 1, 5, 8, 12	Serotonin production will be estimated by measuring the kynurenine/tryptophan ratio in blood collected from participants utilizing a commercially available quantitative immunoassay.
Cortisol	Secondary	Week 1, 5, 8, 12	Urinary cortisol will be estimated utilizing a commercially available quantitative immunoassay.
Inflammatory Markers	Secondary	Week 1, 5, 8, 12	A panel of several serum biomarkers related to inflammation (e.g., C-reactive protein, interleukin-6) will be measured in blood collected from participants utilizing a commercially available quantitative immunoassay.
Mood	Exploratory	Week 1, 3, 5, 8, 10, 12	A validated self-report questionnaire (e.g., the CES-D/CESD R, which ranges from 0-60 points or the PHQ-9, which ranges from 0-27 points)

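### Urinary cortisol and melatonin outcomes pool morning spot and optional 24-hour samples, with no stated common unit, dilution correction or rule that a participant keeps one type

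*Combined protocol and SAP*

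**What the plan says.** - **Spot sample.** Section 5.2 (Spot Urine) plans about 30 mL and explains the timing: "We will aim to collect urine in the morning hours between 8-10 am to avoid the influence of the circadian rhythm on cortisol".
- **Optional sample.** Section 5.2 (24 Hour Urine Sample) says of willing participants that "they will be asked to provide a 24 hour urine collection instead of the planned spot urine collection". They are to "collect all of their urine for the 24 hours preceding select study visits using a provided urine container".
- **Same analytes from both.** The same paragraph continues: "Regardless of whether participants opt for the spot or the 24 hour urine sample, batch analyses of planned urinary biomarkers" will be run, naming cortisol and melatonin as examples. Only the phenolic metabolites are specific to the 24-hour sample.
- **Outcome definitions.** Section 5.4 says "Urinary cortisol will be estimated utilizing a commercially available quantitative immunoassay". Melatonin is defined the same way, through its metabolite 6-sulphatoxymelatonin. Neither entry gives a unit, a creatinine ratio or a collected volume, and section 6.2 adds none.
- **Analysis.** Section 6.2 summarises the change from baseline to follow-up and plans 80% confidence intervals for its SD. Section 6.3 averages the changes within each arm and compares the arms with one paired t-test at 0.05. Neither separates the sample types.
- **Use.** Section 8.6 says later trials will be designed from the variation in change seen here.
- **Schedule.** The optional-assessment table marks "24 Hour Urine Collection" at Weeks 0, 5, 7 and 12. Sections 5.4 and 6.3 use Weeks 1, 5, 8 and 12 for the biomarkers.

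**The concern.** A timed morning sample and a 24-hour pool measure different things. The first is a level at one point of the circadian cycle; the second averages over the whole cycle. The plan fixes the clock time of the first because that cycle matters, then lets the second stand in for it at the participant's choice, with both entering one mean, one SD and one test.

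Three things that would make the mixture manageable are not stated: a common unit, a correction for urine dilution, and a requirement that a participant gives the same type at all four time points.

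These are secondary outcomes, and the primary outcome is feasibility. But producing usable variance estimates is a stated purpose of the pilot. An SD pooled over two quantities describes neither, and a later trial using a single sample type could not be sized from it.

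**Working it through.** **No plan figure to reproduce.** The documents give no power, SD, target effect or derivation of N = 20. The check has two parts: what the text fixes, and what the mixture would do under stated assumptions.

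**Inputs from the documents.** N = 20 in a cross-over (section 3.4); paired t-test at 0.05 (section 6.3; sidedness not stated, two-sided assumed); 240 mL twice per evening in both arms (section 3.2).

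**Assumptions, not document figures.** k participants give 24-hour urine; their values are R times the scale of spot values; the standardised effect is the same on both scales; each participant keeps one type.

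**Step 1: benchmark on one scale.** With n = 20, the paired t-test (noncentral t) has 80% power at a standardised difference of 0.66. With an assumed 16 completers that difference is 0.75.

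**Step 2: mixed scales.** Give each participant a scale s, equal to 1 (spot) or R (24-hour). Then effective n = 20 × (mean s)² / mean(s²), and the pooled SD relative to the spot-only SD is √mean(s²), leaving aside any difference in mean change between the types. For k = 10 and R = 2: mean s = 1.5, mean s² = 2.5, effective n = 20 × 2.25 / 2.5 = 18.0, SD ratio = √2.5 = 1.58. Power comes from 100,000 simulated trials per case, with the effect set at the Step 1 value of 0.66.

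| k of 20 on 24-hour urine | R | Effective n | Power | Pooled SD / spot SD |
|---|---|---|---|---|
| 10 | 2 | 18.0 | 76% | 1.58 |
| 10 | 5 | 13.8 | 63% | 3.61 |
| 10 | 10 | 12.0 | 55% | 7.11 |
| 5 | 2 | 17.9 | 76% | 1.32 |
| 5 | 5 | 11.4 | 56% | 2.65 |
| 5 | 10 | 8.2 | 38% | 5.07 |

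Under no effect, the rejection rate over these cases was 0.031 to 0.049, so it does not rise above nominal.

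**Step 3: uncorrected dilution in spot samples.** On the log scale, if dilution has SD equal to c times the biological SD, the SD of the treatment difference grows by √(1 + c²). For c = 1 this is √2 = 1.41, and power falls from 80% to 51%. For c = 0.6 it is √1.36 = 1.17, and power falls to 67%. The value of c is assumed.

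**Step 4: evening fluid.** The drinks add 2 × 240 = 480 mL each evening during treatment and are absent at baseline. The volume is the same in both arms, so any dilution of follow-up spot urine mainly moves the within-arm change. The documents give no urine volume, so its size cannot be derived.

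**The case against.** Much of the case on the other side stands, and it limits the point.

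- **Bias in the treatment contrast.** A reader might infer that the juice-placebo comparison is invalid. It is not, if each participant keeps one type: both of that person's changes are then on the same scale, and Step 2 shows no inflation of type I error. At R = 2 the power loss is small.
- **Switching type.** The text can be read as a single choice per participant, and nothing plans or invites a switch. What stands is only that no rule forbids one; if it happened between baseline and follow-up, that change could not be interpreted.
- **Raw concentrations.** A reader might infer that spot values will be analysed uncorrected. The documents do not say so; they are silent. Section 8.2 refers data recording to a Manual of Procedures that is not available here and might contain a correction.
- **Log transformation.** Section 6.1 allows transformation, and a log scale would remove a constant unit ratio. It would not remove dilution noise or the difference between a morning and a 24-hour quantity, and it is not specified for this purpose.
- **Size of the dilution shift.** It is tempting to attach a figure. Assumed overnight volumes of 400-800 mL and assumed extra urine of 100-480 mL give falls from 1 − 800/900 = 11% to 1 − 400/880 = 55%. That range comes wholly from the assumptions, treats a visit-time spot as an overnight pool, and largely cancels between products of equal volume.
- **A different baseline week.** The optional table could be read as moving the 24-hour baseline to Weeks 0 and 7. This is most likely labelling. The 3-day diet record has the same marks in the section 5.2 assessment table, and section 5.1 has it completed in the week before the next visit. Consent is obtained only at Week 0, and Week 7 has no visit. A collection just before Weeks 1 and 8 is the coherent reading, and the table only needs to say so.

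**Conclusion.** The concern holds in a limited form. As written, two secondary outcomes combine a morning spot quantity with a 24-hour quantity, with no stated common unit, dilution correction or requirement to keep one sample type. The main harm is to the pooled mean, SD and confidence interval of change, which would describe neither quantity although they are meant to inform later trials.

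There is also a loss of power: from 80% to between 76% and 55% with 10 of 20 on 24-hour urine and ratios of 2 to 10. These figures rest on assumed values of k and R. The documents give neither, and the number choosing 24-hour collection could be zero. Dilution from the evening drinks is a possible further influence on within-arm change, of unknown size.

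This is an inexpensive improvement to secondary outcomes. It does not affect the primary feasibility outcome.

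**What to change.** 1. In section 5.2, collect the 8-10 am spot urine from every participant at Weeks 1, 5, 8 and 12, including those who volunteer for the 24-hour collection.
2. In sections 5.4 and 6.2, define both urinary outcomes from that spot sample, expressed per creatinine.
3. Make the 24-hour collection an addition to the spot sample, used for phenolic metabolites. Report 24-hour cortisol and melatonin metabolite as a sensitivity analysis only.
4. Take the spot sample after the 24-hour collection closes, or account for its volume, so that it does not deplete the 24-hour pool.
5. In the optional-assessment table, state that the Week 0 and Week 7 marks mean collection in the 24 hours before the Week 1 and Week 8 visits, if that is the intention.

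**Cost.** Protocol wording, one extra spot cup for 24-hour volunteers, and creatinine on at most 20 × 4 = 80 samples. The visits already collect morning urine, and the phenolic work is unaffected. The change has to be made before collection, because a spot sample that was never taken cannot be recovered.

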5.3 Dietary Intervention

The duration of this study will be approximately 12 weeks. Throughout the intervention, individuals will be asked to avoid cherry containing foods/beverages.

Individuals will then be randomized to either start with the intervention or the control product. This is a double-blinded study, so the study staff nor the participant will know what juice the participants are assigned to. Those randomized to the intervention group will be asked to consume approximately 8 fluid ounces of tart cherry juice, twice per evening for approximately 4 weeks. Individuals randomized to the control group will be asked to consume approximately 8 fluid ounces of cherry-flavored Kool-aid, that is matched for color, as well as calories and sugar content. Participants will be asked to consume half of their dose (i.e., 8 fluid ounces) at around 5 pm and the remaining half (i.e., 8 fluid ounces) about an hour before bed.

The two juices will be bottled in identical bottles. The placebo will be labeled with a differing letter/number than the intervention product.

At visits 2 and 5, participants will be given an allotment of bottles of their assigned beverage, depending on their ability to store them. These bottles can remain at room temperature until they are opened. Subsequent deliveries will be made by our staff as necessary to ensure participants have a stock of their assigned beverage.

Participants will be given a premeasured cup that indicates how much 8 oz. is to allow participant to easily measure their assigned dose.

5.4 Outcome Measures

Our primary endpoints are aspects of feasibility. Secondary endpoints include sleep quantity and quality, as well as sleep-related biomarkers (e.g., melatonin, serotonin, cortisol, inflammatory markers). Exploratory outcomes include sleep-related factors (e.g., mood, stress, pain). We will also explore other alternative outcomes.

Name	Type	Timeframe	Brief description
Recruitment Rate	Primary	Throughout the entire study	Number of individuals that need to be screened to be enrolled that are randomized to the intervention.
Attrition	Primary	Throughout the entire study	Number of individuals randomized that withdraw from the intervention in media res .
Compliance of Dose	Primary	Throughout the entire study	The number of intended doses consumed.
Ability to Collect Data	Primary	Throughout the entire study	The percentage of missing data points from electronic capture data devices.
Practicality	Primary	Throughout the entire study	Self-reported willingness to continue the dietary regimen after study completion.
Sleep Quantity	Secondary	Throughout the entire study	Individuals will be asked to wear a polysomnographic device (e.g., Garmin

			watch) to continuously measure aspects related to sleep quantity (e.g., total sleep time, time spent awake).
Sleep Quality	Secondary	Week 1, 5, 8, 12	The validated self-report questionnaire, the Pittsburgh Sleep Quality Index, which ranges from 0-21 points.
Melatonin	Secondary	Week 1, 5, 8, 12	Melatonin will be estimated by measuring the major urinary metabolite of melatonin, 6-sulphatoxymelatonin, utilizing a commercially available quantitative immunoassay.
Serotonin	Secondary	Week 1, 5, 8, 12	Serotonin production will be estimated by measuring the kynurenine/tryptophan ratio in blood collected from participants utilizing a commercially available quantitative immunoassay.
Cortisol	Secondary	Week 1, 5, 8, 12	Urinary cortisol will be estimated utilizing a commercially available quantitative immunoassay.
Inflammatory Markers	Secondary	Week 1, 5, 8, 12	A panel of several serum biomarkers related to inflammation (e.g., C-reactive protein, interleukin-6) will be measured in blood collected from participants utilizing a commercially available quantitative immunoassay.
Mood	Exploratory	Week 1, 3, 5, 8, 10, 12	A validated self-report questionnaire (e.g., the CES-D/CESD R, which ranges from 0-60 points or the PHQ-9, which ranges from 0-27 points)
Stress	Exploratory	Week 1, 3, 5, 8, 10, 12	The validated self-report questionnaire, the Perceived Stress Scale, which ranges from 0-56 points.
Pain	Exploratory	Week 1, 3, 5, 8, 10, 12	The validated self-report questionnaire, the Geriatric Pain Measure, which ranges from 0-42 points.

CHAPTER 6. STATISTICAL DESIGN

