Despite 2 successful pilot studies that show tart cherry juice increases sleep quantity in older adults, the underlying mechanisms remain unclear. Tart cherry juice is made from a specific type of cherry variety that is uniquely concentrated with **melatonin**, an important compound involved with the initiation of sleep.¹⁰ Yet, there are also other factors in tart cherries that may impact sleep,¹¹⁻¹⁵ including: **tryptophan**, a precursor to serotonin, a mood regulating hormone,¹⁵⁻¹⁸ **magnesium**, a micronutrient that regulates the production of cortisol, a stress hormone,^{19,20} and **flavonoids**, plant-based compounds that protect cells from damage and lower inflammation in the body (**Figure 1**).^{11,13} Cherry-derived melatonin, tryptophan, magnesium, and

flavonoids all have specific effects on biomarkers, which consequently have downstream effects on sleep-associated factors (i.e., **reduction in core body temperature**,^{10,21,22} **improved mood**,^{18,23-25} **reduced stress**,²⁶⁻²⁸ **and reduced pain**,²⁹⁻³¹ respectively). Clarification of the mechanisms underlying the impact of tart cherry juice on sleep will allow us to ultimately identify other potential foods and/or dietary patterns that provide similar compounds to help with sleep.

CHAPTER 3: RESEARCH DESIGN

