3.1 Study Objectives and Aims

The **overall goal** of this study is to determine feasibility of a tart cherry juice intervention in older adults, and generate preliminary data of outcomes and mechanisms related to sleep. We propose a 2-arm randomized, double-blind, cross-over study in 20 older adults with self-reported insomnia. Participants will consume 240 mL of tart cherry juice or placebo (calorically matched to the tart cherry juice beverage, but theoretically devoid of melatonin, tryptophan, magnesium and flavonoids), twice/evening for approximately 4 weeks in a randomly assigned order. The aims are:

Aim 1: Determine the feasibility of recruiting individuals for and implementing a 4 week tart cherry juice intervention in older adults with self-reported insomnia. Hypothesis: Recruitment for and implementation of a tart cherry juice intervention in older adults with self-reported insomnia is feasible.

Aim 2: Generate preliminary data for sleep quantity, sleep quality, and relevant biomarkers in older adults with self-reported insomnia enrolled in a double-blind randomized placebo controlled tart cherry juice intervention. Hypothesis: Intake of tart cherry juice tends to increase sleep quantity (via sleep monitoring device), sleep quality (via validated questionnaire, e.g., the Pittsburg Sleep Quality Index) urinary melatonin, and serum serotonin, as well as decrease urinary cortisol and serum inflammatory markers.

Exploratory Aim: Explore the impact of tart cherry juice intake on sleep-related factors that may be impacted by the Aim 2 biomarkers in older adults. Hypothesis: Intake of tart cherry juice for 4 weeks results in changes in mood, stress, and pain.

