Biomarkers (i.e., melatonin, serotonin, cortisol, and inflammatory markers) will be measured by a reputable lab (e.g., University of Connecticut) utilizing commercially available quantitative immunoassays (ELISA). **Melatonin** will be estimated by measuring the major urinary metabolite of melatonin, 6-sulphatoxymelatonin. **Serotonin** production will be estimated by measuring the serum kynurenine/tryptophan ratio, which reflects the rate at which tryptophan is converted to kynurenine rather than serotonin.¹⁸ Therefore, lower rates of the kynurenine/tryptophan ratio indicate that more tryptophan is blunted towards the serotonin pathway. **Cortisol** will be estimated by measuring the urinary cortisol. **Serum inflammatory markers** (e.g., interleukins and tumor necrosis factor) will be estimated using a panel of several biomarkers, since inflammation is a heterogeneous/complex process.⁴³ These markers will be consolidated into one composite inflammatory score as previously described.⁴⁴⁻⁴⁶ Change in the biomarker measures will be calculated between baseline and final follow-up visit. The distribution of change in biomarker measures will be summarized using means and standard deviations or medians and interquartile ranges, as appropriate. We will develop 80% confidence interval estimates of inter- and intra- individual variation (i.e., standard deviation) of change in these measures.

Exploratory Outcomes

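### Aim 2 predicts a rise in serum serotonin, but the only measure defined is the kynurenine/tryptophan ratio: an indirect marker that should fall, with a juice constituent as its denominator

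*Combined protocol and SAP*

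**What the plan says.** Section 3.1 states the Aim 2 hypothesis. Among the quantities that juice should tend to increase or decrease it lists "urinary melatonin, and serum serotonin, as well as decrease urinary cortisol and serum inflammatory markers". Serum serotonin is on the increasing side. Chapter 1 also lists serotonin among the biomarkers to be measured.

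The outcome table in Section 5.4 has a secondary outcome called Serotonin, described as follows: "Serotonin production will be estimated by measuring the kynurenine/tryptophan ratio in blood collected from participants". Section 6.2 repeats the definition and explains it: serotonin "production will be estimated by measuring the serum kynurenine/tryptophan ratio, which reflects the rate at which tryptophan is converted to kynurenine rather than serotonin". It then gives the direction: "lower rates of the kynurenine/tryptophan ratio indicate that more tryptophan is blunted towards the serotonin pathway". In Section 5.2, the paragraph on blood samples reads "Batch analyses of planned biomarkers (e.g., kynurenine/tryptophan ratio and select inflammatory markers" and names no serotonin assay.

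On the products, Chapter 2 names tryptophan as a constituent of tart cherries and calls it "a precursor to serotonin, a mood regulating hormone". Section 3.1 describes the placebo as "calorically matched to the tart cherry juice beverage, but theoretically devoid of melatonin, tryptophan, magnesium and flavonoids".

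Section 6.3 compares changes between juice and placebo with a paired t-test at 0.05. For the exploratory aim it correlates changes in mood, stress and pain with changes in biomarkers by Spearman's method. It gives no expected sign for either analysis.

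**The concern.** The hypothesis and the endpoint are different quantities. Serotonin is neither the numerator nor the denominator of the ratio, so the ratio carries information about serotonin only by inference. The name and the sign also pull apart: an outcome called Serotonin, predicted to rise, is represented by a variable that should fall.

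The denominator is also a compound that, by design, one product supplies and the other in principle does not. A lower ratio on juice could mean that less tryptophan is being converted to kynurenine, or only that more tryptophan is circulating. The ratio alone cannot tell these apart, and neither reading shows that serum serotonin changed.

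At stake is what the trial can say about one of its four biomarker outcomes (melatonin, serotonin, cortisol, inflammatory markers). Section 8.6 says that the variation in change observed here will be used to design later trials, so a label that the measurement does not support could be carried forward.

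**Working it through.** **Hypothesis against definition.** The documents give no power or effect-size figure for this outcome, so there is none to reproduce. The places that bear on it compare as follows.

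| Place | Quantity named | Direction stated |
|---|---|---|
| 3.1, Aim 2 | Serum serotonin | Increase |
| 5.2, blood samples | Kynurenine/tryptophan ratio | None |
| 5.4, Serotonin row | Kynurenine/tryptophan ratio, as an estimate of serotonin production | None |
| 6.2, biomarkers | Serum kynurenine/tryptophan ratio, as an estimate of serotonin production | Lower means more towards serotonin |
| 6.3, analysis | Change in the measures of 6.2 | None |

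The list in 5.2 is introduced as examples, so alone it would not exclude a serotonin assay. The definitions in 5.4 and 6.2 are not worded as examples, and they settle the point.

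**Effect of tryptophan supply on the ratio.** Let R = K/T, with K kynurenine and T tryptophan. Suppose T rises by a fraction r and K is multiplied by (1 + r)^e. Then e = 0 means that kynurenine does not respond, e = 0.5 that it rises half as much on the log scale, and e = 1 that it rises in proportion. The relative change in R is

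(1 + r)^e / (1 + r) − 1 = (1 + r)^(e − 1) − 1.

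The documents give neither the tryptophan content of a dose nor a blood response, so r and e are both assumptions. Two worked cases with e = 0: for r = 0.05, 1/1.05 − 1 = −4.8%; for r = 0.10, 1/1.10 − 1 = −9.1%. The wider range is:

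| Assumed rise in T | e = 0 | e = 0.5 | e = 1 | e = 1.2 |
|---|---|---|---|---|
| 5% | −4.8% | −2.4% | 0 | +1.0% |
| 10% | −9.1% | −4.7% | 0 | +1.9% |
| 20% | −16.7% | −8.7% | 0 | +3.7% |
| 30% | −23.1% | −12.3% | 0 | +5.4% |

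The ratio falls only when kynurenine rises less than tryptophan (e < 1). Serotonin does not appear in the formula, so any of these changes can occur with serotonin constant.

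**Sampling.** Section 5.2 specifies fasted blood drawn between 8 and 10 am, while the doses are taken the evening before. This may reduce a direct intake effect; the documents do not show by how much.

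**The case against.** The strongest reply is that the plan already discloses most of this. Sections 5.4 and 6.2 both call the ratio an estimate, and Section 6.2 gives its inverse direction in plain terms. Melatonin too is estimated indirectly, through a urinary metabolite. Aim 2 likewise predicts an increase in sleep quality although a higher Pittsburgh score is worse, so an inverse scale is not unusual in this plan. A paired t-test is valid whatever sign is expected, and a Spearman coefficient for an inverse marker only changes sign. Higher tryptophan is also the first step of the route proposed in Chapter 2, so it is not purely a nuisance. Finally, the size of the intake effect is unknown and may be nil.

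All of that stands, and it limits the point. It does not remove the mismatch between serum serotonin in Aim 2 and a ratio that does not contain serotonin. Nor does the proposed mechanism rescue the label: if tryptophan rises because the juice supplies it, the ratio partly records exposure to the product and still does not show that serotonin rose.

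Three stronger readings are tempting, and the documents do not support them.

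- A reader might infer that the plan has the direction wrong or hides it. It does not: Section 6.2 states it.
- A reader might infer that the serotonin mechanism cannot be supported at all. The ratio remains indirect evidence on the pathway, and the alternative explanation is a possibility of unknown size.
- A reader might infer that only a fall driven by lower kynurenine should count. Nothing in the documents sets that criterion, and it would exclude the precursor route that Chapter 2 proposes.

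**Conclusion.** The point holds as a matter of labelling and interpretation in a secondary outcome. As worded, the serotonin part of Aim 2 cannot be tested, because no serotonin measurement is defined. The ratio should fall if the hypothesis is true; Section 6.2 says this, but Aim 2 and the Section 5.4 table do not. The ratio can also fall because circulating tryptophan is higher on juice, without a change in serotonin.

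That last statement rests on two features of the plan, tryptophan named in the juice and in principle absent from the placebo, and on kynurenine rising less than tryptophan. The calculated falls are illustrations under assumed responses, not estimates for this trial. One of four biomarker outcomes is affected. The planned tests remain valid as tests of the ratio, and the primary feasibility outcomes are untouched.

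**What to change.** In Sections 3.1, 5.4 and 6.2, name the outcome *kynurenine/tryptophan ratio (indirect marker of serotonin production)* and give a decrease as the expected direction. Bring the mention of serotonin in Chapter 1 into line.

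In Sections 6.2 and 6.3, add that kynurenine and tryptophan will each be analysed and reported beside the ratio, with the same change summaries. A reader can then see whether a change in the ratio comes from the numerator, the denominator or both.

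State in advance that any result will be described as indirect evidence on the tryptophan–serotonin pathway, not as a change in serum serotonin.

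The cost is small. Forming the ratio already needs both component values, so no visit, sample or assay is added. The work is wording and two more reported variables. The trial gives up a direct claim about serotonin.
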